**COMPARISON OF THE ACCURACY OF MONITORING DEVICES IN PREDICTION OF
FLUID RESPONSIVENESS IN SEVERE SEPSIS AND SEPTIC SHOCK**

PRINCIPAL INVESTIGATOR: [name]

DATE OF PROTOCOL: 12/29/2016

VERSION 3

BACKGROUND

One of the most challenging problems in critical care is determination of whether patients have adequate intravascular volume, and whether they would benefit from additional intravenous fluids. Giving too much fluid to patients with adequate intravascular volume could lead to fluid overload, congestive heart failure and subsequent respiratory failure. Not giving enough fluid to

patients, risks leaving them under-resuscitated and worsening their shock state, leading to organ failures, such as kidney failure. Clinically, it is very difficult to determine this “intravascular volume status”, and predict which patients would benefit from more fluid. One of the ways we currently determine this, is to measure cardiac output and one of its main components, stroke volume (how much blood is pumped by the heart each beat) and see whether these increase in response to a passive leg raise (PLR) maneuver¹. The maneuver is simple, quick, with essentially no risk. The maneuver involves measuring baseline cardiac output and stroke volume with the patient’s head up at 45 degrees and legs flat for 3 minutes. Subsequently, the head is placed flat and the legs are raised to 45 degrees for 3 minutes. If the cardiac output and stroke volume increase in response to this maneuver, there is a high probability that the patient will have a good response to giving intravenous fluid.

Currently there are multiple FDA approved devices which can be used to measure cardiac output and stroke volume, ranging from very invasive (pulmonary artery catheter), to minimally invasive (requiring arterial catheter +/- central venous catheter- Flotrac, PICCO)^{3,4} to a newer, completely non- invasive device, called the NICOM (Cheetah). The FloTrac is a commonly used device for assessment of fluid status in the ICU, but to date has not been validated in predicting volume responsiveness of patients with sepsis or septic shock, although it has been validated in a number of other clinical settings. The monitor is able to determine stroke volume, heart rate, cardiac output, and other hemodynamic information.

OBJECTIVES

The most commonly used device for hemodynamic monitoring at Cottage is the Edwards FloTrac monitor, which requires arterial catheterization. Use of this device is our standard practice in treating patients with septic shock, with virtually all of our patients requiring the device both for continuous arterial pressure monitoring, as well as determination of cardiac output and stroke volume, and prediction of fluid responsiveness as described above. Unfortunately, it is well known that use of the FloTrac in septic patients is problematic, due to the state of their blood vessels from the disease state, as well as the effect of medications we use to treat their low blood pressure. We would like to test the accuracy of the FloTrac device in septic patients.

This study is designed to test the ability of the Flotrac device to predict the need for fluid administration in septic shock patients, requiring medications (vasopressors) to support their blood pressure. We will be using the measurements of cardiac output and stroke volume derived from the FloTrac, in conjunction with the passive leg raise test described above. Patients whose measurements suggest a need for more fluid with one or both devices, will receive a standard intravenous fluid bolus. Additionally, any patient who the treating clinician feels a fluid bolus is clinically indicated, regardless of the results of the PLR, will receive a fluid bolus. Clinicians may use ultrasound imaging of the inferior vena cava, or any other clinical information they routinely use, to make this determination. In this way false positives and false negatives will be apparent with both devices.

STUDY POPULATION

50 patients will be studied. Patients may have one or multiple assessments during their ICU stay as clinically indicated.

Inclusion Criteria:

- All adult patients with severe sepsis with hypotension, or septic shock, who have an arterial catheter with Flotrac monitor, with or without a central venous catheter, will be eligible for inclusion in the study.

Exclusion Criteria:

- Patient or legally authorized representative (LAR) decline consent.
- Pregnancy.
- Contraindication to raising legs or head to 45 degrees for 3 minute intervals.

Withdrawal and termination criteria:

- Patients may ask to withdraw from the study at any time.
- Termination criteria would include removal or malfunctioning of arterial catheter or Flotrac device. Resolution of hypotension or shock state, and discharge or transfer from the ICU.

STUDY METHODS AND PROCEDURES

This will be a prospective, non-blinded, non-randomized study. Identification of appropriate patients meeting inclusion criteria, will be made by house staff and medical attending staff. Patients or their LAR will be asked to participate and sign consent, if in agreement.

When the clinical team feels assessment of intravascular volume status is appropriate, a passive leg raise maneuver (PLR) (see figure 1) will be performed, and clinical and hemodynamic variables (see data collection sheet- figure 2) will be recorded by the physicians and/or critical care nurse performing the maneuver. All patients will get a single fluid challenge after the initial PLR assessment, regardless of the result of the PLR. This fluid challenge can be cancelled by the treating physician based on clinical judgement. A physician may wish to cancel this fluid challenge if there is a risk of fluid overload with the patient. This fluid challenge will help us determine a false negative rate. After the first PLR, subsequent fluid challenges will only be given if the patient has greater than or equal to 10% increase in any of the 3 listed parameters, SVI, CI, or PP. PLRs will be done every 6 hours routinely (Figure 3), and additionally, if ordered by the physician. A physician can also order a fluid challenge at any time, based on clinical judgement regardless of PLR result. The fluid challenge will consist of intravenous administration of 500 ml of crystalloid solution (either saline or plasmalyte) given as rapidly as possible via a pressure bag, as is standard practice. If in the judgment of the treating physician, a smaller amount would be safer, the patient can be given a 250 ml bolus. Alternatively, the

patient may be given a bolus of either 250, or 500 ml of 5% albumin administered at the maximum IV infusion pump rate of 1200 ml/hr.

The type of fluid, volume, and duration of infusion of the fluid challenge will be recorded. Following the fluid challenge, the patient's hemodynamic response will be recorded, with the patient in the semi-upright 45 degree head up position.

During the above maneuvers, in accordance with standard practice, doses of vasopressors and mechanical ventilation settings (if on a ventilator) will be recorded and maintained constant, so as not to effect the measurements.

RISKS AND BENEFITS

We do not anticipate any significant risks to the patient from the study. There is a remote risk of excessive fluid administration with the Flotrac device, but this risk is routinely present outside of the study. However, while the Flotrac device is routinely used with PLR for assessing fluid responsiveness in our ICU, it also has not been adequately studied in septic patients. It should be kept in mind that fluid challenges are routinely given in this patient population based on clinical factors other than indicated by these devices. These clinical factors include central venous pressure, respiratory variation of inferior vena cava caliber by ultrasound, fluid balance, clinician "gestalt", etc. Such fluid challenges are considered diagnostic, potentially therapeutic and generally safe, and may be given during this study, if the treating physician feels they are indicated. Therefore, we do not feel there is any additional risk posed by this study.

CLINICAL DATA MANAGEMENT

See the attached data collection tool. In addition to the data sheet, routine data collected on all septic patients as part of the IRB approved SBCH Sepsis registry will be collected. We will also collect information on comorbidities which could impact the results, such as presence of heart failure. Echocardiogram results, if any, will also be collected as part of this process.

The data will be transferred from the data collection tools to Redcap database management system. The original data sheets will be kept on the SBCH premises in a locked cabinet.

All data will be reported in a collective fashion, without any unique patient identification.

[figure not shown]
STATISTICAL ANALYSIS

The predictive value of fluid responsiveness by the Flotrac device will be compared in the primary assessment. Other data accumulated during the trial, such as CVP, blood pressures (including MAP and pulse pressure), ultrasound assessment of IVC for fluid responsiveness will also be analyzed, secondarily. The ability of Flotrac to assess fluid responsiveness will be analyzed using the Receiver Operating Characteristic paradigm.

REFERENCES

1. Monnet X and Teboul JL. Passive leg raising: Five rules, not a drop of fluid. *Critical Care* 2015; 19:18

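### The number of leg-raise assessments per patient depends partly on shock duration, and the ROC analysis states no unit of analysis and no handling of repeats

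*Combined protocol and SAP*

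**What the plan says.** - **Sample size and repeats (Study Population).** The plan states "50 patients will be studied" and adds "Patients may have one or multiple assessments during their ICU stay as clinically indicated". No number of assessments is given and there is no cap.
- **Schedule (Study Methods and Procedures).** "PLRs will be done every 6 hours routinely (Figure 3), and additionally, if ordered by the physician".
- **End of participation (Withdrawal and termination criteria).** "Termination criteria would include removal or malfunctioning of arterial catheter or Flotrac device", followed by "Resolution of hypotension or shock state, and discharge or transfer from the ICU". Patients may also withdraw.
- **Which assessments get a reference outcome (Study Methods and Procedures).** The first PLR is followed by a fluid challenge whatever its result, unless the physician cancels it. Later PLRs are followed by a challenge only after a rise of at least 10% in SVI, CI or PP, or on a physician's order.
- **Why the device is in doubt (Objectives).** FloTrac is called problematic in septic patients "due to the state of their blood vessels from the disease state, as well as the effect of medications we use" to treat low blood pressure.
- **Analysis (Statistical Analysis).** "The ability of Flotrac to assess fluid responsiveness will be analyzed using the Receiver Operating Characteristic paradigm". Nothing is said about the unit of analysis, weighting or correlation within a patient.

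**The concern.** The number of assessments per patient is partly an outcome of the illness, because a patient who stays in shock goes on being assessed. This is informative cluster size, and it has two consequences if every challenged assessment enters one ROC curve as an independent observation.

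First, readings from one patient are likely to be correlated, so the usual interval would be too narrow. Second, the curve would describe the average challenged PLR rather than the average patient, with patients in longer shock counting for more. A cluster-robust interval repairs the first problem and leaves the second. If accuracy differs with shock duration, the headline figure would depend on how long the enrolled patients happened to stay in shock, even with no change in the device.

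**Working it through.** The plan's own figure of 50 patients cannot be reproduced, because no target AUC, power, responder prevalence or number of assessments is given. Only the 50 patients, the 6-hour interval and the challenge rule below come from the protocol. Durations, challenge fractions, correlations and accuracies are assumptions.

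**1. Assessments per patient.** With shock lasting T hours and no extra PLRs, m = 1 + floor(T/6). So 12 h gives 3, 24 h gives 5, 48 h gives 9, 72 h gives 13 and 96 h gives 17.

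**2. Share from the longer-shock half.** If a fraction f of later PLRs is challenged, a patient contributes 1 + f(m − 1) analysable assessments. For 12 h against 72 h at f = 0.25, the short patient gives 1 + 0.25 × 2 = 1.5 and the long patient 1 + 0.25 × 12 = 4. The long share is 4/5.5 = 73%.

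| Short vs long shock | f = 0 | f = 0.1 | f = 0.25 | f = 0.5 | f = 1 |
|---|---|---|---|---|---|
| 12 h vs 72 h | 50% | 65% | 73% | 78% | 81% |
| 24 h vs 96 h | 50% | 65% | 71% | 75% | 77% |
| 24 h vs 48 h | 50% | 56% | 60% | 62.5% | 64% |

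Durations were also simulated for 50 patients (exponential, or lognormal with log-SD 0.8; means 24 to 72 h). The longer-shock half supplies 65–76% at f = 0.25 and 75–83% at f = 1. The extra weight disappears only at f = 0.

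**3. Interval.** An approximate design effect is 1 + ((cv² + 1)m̄ − 1)ρ, where m̄ and cv are the mean and coefficient of variation of analysable assessments per patient. With an assumed within-patient correlation ρ = 0.3, the same simulations give 1.40 to 2.53 at f = 0.25 and 2.94 to 7.74 at f = 1. Taking square roots, a standard error that assumes independence is too small by a factor of about 1.2 to 1.6, or 1.7 to 2.8. With ρ = 0 there is no understatement.

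**4. Point estimate, ignoring how later PLRs are selected.** Moving the long-shock share from 50% to 81% takes a pooled AUC from 0.75 to 0.69 if the AUC is 0.85 in short and 0.65 in long shock. It goes from 0.80 to 0.77 if the AUCs are 0.85 and 0.75. It stays at 0.80 if both are 0.80. This shows the direction and the condition for a shift, not its size in this trial.

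**5. Point estimate under the protocol's challenge rule.** Take equal numbers of patients with 3 and 16 PLRs, with true sensitivity and specificity both 0.85 in the first group and both 0.65 in the second. The patient average is (0.85 + 0.65)/2 = 0.75. Treat the 10% rule as the test, always challenge the first PLR, hold responder prevalence constant, and challenge later negatives with probability g. Counts below are expected values, scaled to one responder or one non-responder per PLR.

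- g = 0, sensitivity: true positives 3 × 0.85 + 16 × 0.65 = 12.95. Challenged responders (1 + 2 × 0.85) + (1 + 15 × 0.65) = 13.45. Ratio 0.96.
- g = 0, specificity: true negatives 0.85 + 0.65 = 1.50. Challenged non-responders (1 + 2 × 0.15) + (1 + 15 × 0.35) = 7.55. Ratio 0.20.
- g = 0.2, sensitivity: challenged responders (1 + 2 × 0.88) + (1 + 15 × 0.72) = 14.56. Ratio 12.95/14.56 = 0.89.
- g = 0.2, specificity: true negatives (0.85 + 2 × 0.2 × 0.85) + (0.65 + 15 × 0.2 × 0.65) = 3.79. False positives 3 × 0.15 + 16 × 0.35 = 6.05. Ratio 3.79/9.84 = 0.39.

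The equal-weight column comes from simulation of the same set-up:

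| Sensitivity / specificity | All challenged, unweighted | Equal weight per patient | First PLR only |
|---|---|---|---|
| g = 0 | 0.96 / 0.20 | 0.95 / 0.40 | 0.75 / 0.75 |
| g = 0.2 | 0.89 / 0.39 | 0.90 / 0.53 | 0.75 / 0.75 |

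Equal weighting alone does not recover the patient average once later PLRs enter selectively. The first PLR does, provided its challenge is not cancelled selectively.

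**The case against.** The strongest reply is that the plan never says assessments will be pooled, and that accuracy per PLR performed is a legitimate target. Both points stand. Pooling is a risk left open by silence, and the defect is that the unit is unstated, not that one unit is wrong in itself.

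Three stronger readings are tempting, and the documents do not support them.

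- **The protocol expects FloTrac to work worst in long shock.** It does not say so. The Objectives call the device problematic in septic patients generally, and the target population already requires vasopressors. More vasopressor exposure in longer shock is plausible, but it is an inference.
- **A definite bias can be quoted, such as pooled sensitivity of 0.68 against a patient average of 0.75.** With 3 and 16 PLRs and sensitivities of 0.85 and 0.65, (3 × 0.85 + 16 × 0.65)/19 = 0.68. That requires every PLR to be challenged, or challenges to be unrelated to the PLR result. The Methods rule out both.
- **A patient whose hypotension resolves during a bolus is lost before the post-challenge reading.** The Methods say the response is recorded after the challenge, the data sheet (Figure 2) has a row for it, and nothing says termination interrupts a challenge. A rise in SVI or CI is also not the same as resolution of shock.

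It is also true that device loss, ICU discharge or transfer, and withdrawal end assessments, and that extra PLRs may be ordered. These loosen the link with shock duration but do not remove it.

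**Conclusion.** The point holds in a limited form. The number of assessments depends partly on shock duration, and the plan gives no unit of analysis or handling of repeats. If challenged assessments were pooled as independent, positive within-patient correlation would make the interval too narrow, and longer-shock patients would be over-weighted whenever some later PLRs are challenged. For the duration pairs examined, the longer-shock half would carry 60–73% of the weight at f = 0.25 and 64–81% at f = 1.

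This weighting moves the point estimate only if accuracy is related to duration. The stated vasopressor effect gives some reason to suspect that, but the protocol does not assert it. The size cannot be derived from the documents, since durations, the fraction challenged and the accuracies are all unknown. In the illustration, selective challenge of later PLRs distorts sensitivity and specificity more than unequal counts do, so the remedy has to deal with both.

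**What to change.** In the Statistical Analysis section:

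1. Make the primary ROC one assessment per patient, using the first PLR, the one planned to be challenged whatever its result. Report how many first challenges were cancelled, with reasons.
2. Analyse all challenged assessments secondarily. Give each a weight of 1/(number of that patient's analysed assessments), take the interval from a bootstrap that resamples patients, and show the unweighted estimate alongside. Label these results as subject to selective challenge of later PLRs.
3. Reconcile assessments as clinically indicated (Study Population) with routine 6-hourly PLRs (Study Methods and Procedures), since the two imply different counts. The Objectives also describe boluses only after a positive PLR or on clinician judgement, without the universal first challenge on which item 1 relies. Those passages should be reconciled too.

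The change is to wording, with no extra data collection. The cost is an interval wider than a naive pooled analysis would give. As a guide, for an assumed AUC of 0.80 and all 50 first PLRs challenged, the Hanley–McNeil variance with 25 responders and 25 non-responders is [0.16 + 24 × (0.6667 − 0.64) + 24 × (0.7111 − 0.64)]/625 = 0.0040. The standard error is 0.063 and the 95% half-width about 0.12. With 15 responders and 35 non-responders it is [0.16 + 14 × 0.0267 + 34 × 0.0711]/525 = 0.0056, a half-width of about 0.15. Cancelled first challenges would widen this further.

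### The first fluid challenge may be cancelled after the PLR result is known, so the false-negative rate and the ROC analysis are open to partial verification bias that the plan neither records nor corrects

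*Combined protocol and SAP*

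**What the plan says.** Under Study Methods and Procedures the default is universal verification at the first assessment: "All patients will get a single fluid challenge after the initial PLR assessment, regardless of the result of the PLR". The purpose is given too: "This fluid challenge will help us determine a false negative rate".

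Between these two statements stands the exception: "This fluid challenge can be cancelled by the treating physician based on clinical judgement". One ground is offered, as an example rather than a limit: "A physician may wish to cancel this fluid challenge if there is a risk of fluid overload with the patient". The text does not say when the decision is taken, or whether the PLR result may inform it.

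The same section describes the design: "This will be a prospective, non-blinded, non-randomized study". The PLR readings "will be recorded by the physicians and/or critical care nurse performing the maneuver", so they are known at the bedside before the challenge.

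After the first PLR the default reverses: "subsequent fluid challenges will only be given if the patient has greater than or equal to 10% increase in any of the 3 listed parameters". There is one other route to a challenge after a negative PLR: "A physician can also order a fluid challenge at any time, based on clinical judgement regardless of PLR result". The Objectives section likewise relies on clinician-indicated boluses to reveal false negatives.

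Statistical Analysis names the predictive value of the device as the primary assessment and ROC as the method. It does not say how a PLR without a following challenge is handled, and the false-negative rate is not defined. The data sheet in Figure 2 has fluid type, amount and infusion time, but no entry for a cancelled challenge, its reason or its timing.

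**The concern.** The first challenge is the only one given by default after a negative PLR, so it is the best source of reference results for PLR-negative patients. An unblinded physician may cancel it, possibly with the PLR result in hand. A cancelled patient has an index test and no reference result, and drops out of any analysis restricted to challenged patients.

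It is plausible that cancellation is more common after a negative PLR. The Background links fluid given to a patient with adequate volume to overload, which is the ground named for cancelling, and the protocol itself makes a PLR rise the default condition for later challenges. If so, false negatives and true negatives are lost more often than true and false positives, and the ROC curve is distorted. Restricting the analysis to first PLRs would not remove this, because the selection acts on the first PLR itself.

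**Working it through.** The plan states no false-negative rate, so there is no figure to reproduce. The check asks what cancellation does to a 2×2 table.

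**Inputs.** From the documents: 50 patients (Study Population), each with one default first challenge. Not in the documents, and therefore assumed: half are true responders, true sensitivity and specificity are 0.80, and the cancellation rates are as shown. A positive PLR is taken as the 10% rise that the protocol uses for later challenges. The full table is TP 20, FN 5, FP 5, TN 20.

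**Formulas.** Let v₊ and v₋ be the proportions actually challenged after a positive and a negative PLR.
- Observed sensitivity = v₊TP / (v₊TP + v₋FN)
- Observed specificity = v₋TN / (v₋TN + v₊FP)
- FN among PLR-negatives = v₋FN / (v₋FN + v₋TN) = FN / (FN + TN); v₋ cancels out

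**Cancellation depends on the PLR result only; 5% of positives cancelled (v₊ = 0.95), except in the first row**

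| Negatives cancelled | TP, FN, FP, TN left | Sensitivity | 1 − sensitivity | Specificity | FN among PLR-negatives |
|---|---|---|---|---|---|
| No cancellation at all | 20, 5, 5, 20 | 0.80 | 0.20 | 0.80 | 5/25 = 0.20 |
| 20% | 19, 4, 4.75, 16 | 19/23 = 0.83 | 0.17 | 16/20.75 = 0.77 | 4/20 = 0.20 |
| 40% | 19, 3, 4.75, 12 | 19/22 = 0.86 | 0.14 | 12/16.75 = 0.72 | 3/15 = 0.20 |
| 60% | 19, 2, 4.75, 8 | 19/21 = 0.90 | 0.10 | 8/12.75 = 0.63 | 2/10 = 0.20 |

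The shift in 1 − sensitivity does not depend on the proportion of responders. With no positives and half the negatives cancelled, a true value f is observed as 0.5f / (0.5f + 1 − f): 0.10 becomes 0.05/0.95 = 0.053, and 0.30 becomes 0.15/0.85 = 0.176.

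**Other cancellation patterns, same full table**

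| Pattern | TP, FN, FP, TN left | 1 − sensitivity | Specificity | FN among PLR-negatives |
|---|---|---|---|---|
| 30% of everyone | 14, 3.5, 3.5, 14 | 3.5/17.5 = 0.20 | 0.80 | 0.20 |
| 20% of positives, 10% of negatives | 16, 4.5, 4, 18 | 4.5/20.5 = 0.22 | 18/22 = 0.82 | 0.20 |
| 40% of non-responders, 10% of responders, whatever the PLR | 18, 4.5, 3, 12 | 4.5/22.5 = 0.20 | 12/15 = 0.80 | 4.5/16.5 = 0.27 |
| PLR-negative: 50% of non-responders, 20% of responders; PLR-positive: 10%, 0% | 20, 4, 4.5, 10 | 4/24 = 0.17 | 10/14.5 = 0.69 | 4/14 = 0.29 |

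So 1 − sensitivity is too low only if responders are cancelled more often after a negative than after a positive PLR. FN among PLR-negatives moves only if cancellation among negatives is related to true response.

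**Does a correction work?** Begg-Greenes divides each verified count by the proportion challenged in its PLR group. In the 40% row, FN = 3/0.60 = 5 and TP = 19/0.95 = 20, which returns 5/25 = 0.20. In the pattern driven by true response (40% against 10%), the proportions challenged are (18 + 3)/25 = 0.84 and (4.5 + 12)/25 = 0.66. Then FN = 4.5/0.66 = 6.82 and TP = 18/0.84 = 21.43, so the corrected value is 6.82/28.25 = 0.24 although the uncorrected 0.20 was right.

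**Bounds in the 40% row** (1.25 positives and 10 negatives cancelled). All counted as responders: 1 − sensitivity = 13/33.25 = 0.39, specificity 12/16.75 = 0.72. All counted as non-responders: 3/22 = 0.14 and 22/28 = 0.79. These two fills miss the true specificity of 0.80, so they are not the outer limits. Those come from opposite allocation:
- Cancelled negatives as responders, cancelled positives as non-responders: 13/32 = 0.41 and 12/18 = 0.67.
- The reverse: 3/23.25 = 0.13 and 22/26.75 = 0.82.

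**The case against.** A reader might infer three stronger things, none of which the documents support.

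- **That the PLR result does select who is challenged, so the false-negative rate will come out too low.** The only ground named is overload risk, which may be known before any PLR, and the timing of the decision is not stated. Cancellation unrelated to PLR and response costs verified patients (35 of 50 at 30%) but gives no bias, and more cancellation after positives reverses the direction. If the undefined rate means FN among PLR-negatives, cancellation by PLR result alone leaves it unchanged. That is a fair reading, since predictive value is named as the primary assessment.
- **That the first challenge is the only source of false negatives.** Clinician-ordered challenges after a negative PLR are also allowed. They are selected too, so they cannot replace the first challenge, but they exist.
- **That the loss cannot be described or corrected.** If Figure 2 is completed as laid out, a first trial with PLR readings and an empty challenge block identifies the unverified patient and the PLR result. That is enough for the basic correction. Clinical Data Management also collects heart failure and any echocardiogram results. What is missing is the reason and the timing.

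The option of a smaller bolus may also reduce the number of cancellations. The assumed rates come from outside the documents, and at 20% cancellation of negatives the 3-point shift is small beside the exact 95% interval of 0.59 to 0.93 for 20/25.

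These objections limit the claim about direction and size. They do not remove the opening for bias: sensitivity and specificity are what an ROC analysis uses, and the plan has no rule for unverified patients.

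**Conclusion.** The point holds conditionally. The plan allows the reference result at the first PLR to depend on the index test, and has neither a record of why a challenge was cancelled nor an analysis that allows for it. If challenges are cancelled more often after a negative PLR, the complete-case ROC overstates sensitivity and understates specificity.

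The mechanism follows from the text, the direction is plausible but inferred, and the size cannot be derived. On the assumptions above (5% of positives and 20% to 60% of negatives cancelled, independently of true response within each PLR group), a true 1 − sensitivity of 0.20 would be observed as 0.17 to 0.10. The change should be made while data are still being collected, because reasons and timing may not be recoverable later.

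**What to change.** The physician's freedom to cancel at any time stays as it is. Only recording and analysis change.

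1. Add a line to the Figure 2 sheet: first challenge cancelled (yes/no), reason, and whether this was decided before or after the PLR result was known. Where feasible, record the physician's intention before the PLR starts.
2. Define the false-negative rate as 1 − sensitivity, and report FN among PLR-negatives beside it.
3. Report the number and proportion challenged, by PLR result.
4. Beside the complete-case ROC, report a Begg-Greenes or inverse-probability-weighted estimate. State its assumption that cancellation depends only on the PLR result and recorded covariates. For the full curve, base the weights on the measured PLR change rather than on positive/negative alone.
5. Report bounds with all cancelled patients counted as responders, then as non-responders. Add the two opposite allocations by PLR result, which give the outer limits for sensitivity and specificity.

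The cost is one line on the data sheet, a few sentences in the methods and a small extra analysis. The weighted intervals will be slightly wider. No extra patients or procedures are needed.

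### The ROC analysis is not limited to first PLRs, the only ones where PLR-negatives are routinely fluid-challenged; pooling every challenged assessment would understate specificity and overstate sensitivity

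*Combined protocol and SAP*

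**What the plan says.** Study Methods and Procedures sets two rules for the reference standard, which is the response to a fluid challenge.

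- **First PLR.** Every patient is challenged whatever the PLR shows. The section gives the purpose: "This fluid challenge will help us determine a false negative rate". There is one exception: "This fluid challenge can be cancelled by the treating physician based on clinical judgement".
- **Later PLRs**, routinely six-hourly. "After the first PLR, subsequent fluid challenges will only be given if the patient has greater than or equal to 10% increase in any" of SVI, CI or PP. There is one other route: "A physician can also order a fluid challenge at any time, based on clinical judgement regardless of PLR result".

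Objectives describes the trigger differently. A bolus follows a suggestive measurement on either or both of two devices, or a clinician's judgement. It then concludes: "In this way false positives and false negatives will be apparent with both devices". The same section bases the test on FloTrac output: "We will be using the measurements of cardiac output and stroke volume derived from the FloTrac".

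Study Population sets 50 patients and adds: "Patients may have one or multiple assessments during their ICU stay as clinically indicated".

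Statistical Analysis names the ROC method for FloTrac and makes pulse pressure secondary. It defines no analysis set or unit of analysis, does not restrict the ROC to first PLRs, and does not mention assessments without a challenge. The data sheet (Figure 2) has a TRIAL # field and a fluid-challenge block.

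**The concern.** Sensitivity, specificity and the ROC curve need the reference result in test-negatives as well as test-positives. The design provides this at the first PLR, apart from cancellations. At later PLRs the test result itself largely decides who gets the reference standard. Positives are challenged by rule. Negatives are challenged only if another parameter crosses 10% or a clinician chooses to act.

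The documents point two ways on which data supply the false negatives. Study Methods and Procedures looks to the universal first challenge; Objectives looks to the selected set of boluses. Statistical Analysis does not choose between them. Accuracy is the study's primary aim, so the choice of analysis set could shift the main result, and it is at present open to being made after the data are seen. Adding later PLRs would not dilute the problem; it would increase it.

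**Working it through.** **Plan's own figure.** The 50 patients come with no expected accuracy, precision or power, so there is nothing to reproduce.

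**Inputs from the documents.** 50 patients; full verification at the first PLR; later verification by a ≥10% rise in any of SVI, CI or PP, or by order.

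**Assumed inputs, since the documents give none.** True sensitivity (Se) and specificity (Sp) 80% for each parameter; 50% responders at every PLR; no first-challenge cancellations; SVI as the tested parameter; k = 3 later PLRs per patient; 0% or 25% of all-negative later PLRs challenged on order. The three signals are trivariate normal, with SVI–CI correlation 0.8–0.95 and PP with either 0.3–0.7.

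**Direction.** Let v_R and v_N be the fractions of later SVI-negative responders and non-responders who are challenged. Later SVI-positives are all challenged. Then

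- pooled Se = Se(1+k) / [Se(1+k) + (1−Se)(1+k·v_R)]
- pooled Sp = Sp(1+k·v_N) / [Sp(1+k·v_N) + (1−Sp)(1+k)]

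Whenever v_R and v_N are below 1, pooled Se exceeds Se and pooled Sp falls below Sp.

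**Worked case, correlations 0.9 and 0.5.** With no orders, CI or PP triggers a challenge in v_R = 0.643 of SVI-negative responders and v_N = 0.184 of SVI-negative non-responders. Expected counts:

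- TP = 20 × 4 = 80; FP = 5 × 4 = 20
- FN = 5 × (1 + 3 × 0.643) = 14.65; TN = 20 × (1 + 3 × 0.184) = 31.03 (unrounded fractions used)
- Se = 80/94.65 = 84.5%; Sp = 31.03/51.03 = 60.8%; NPV = 31.03/45.68 = 67.9%; PPV = 80/100 = 80%

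With 25% of all-negatives challenged, FN = 15.99 and TN = 43.27, so Se is 83.3%, Sp 68.4% and NPV 73.0%.

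**Across the correlation sets** (three later PLRs):

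| All-negatives challenged | Se | Sp | LR+ | LR− | NPV | AUC |
|---|---|---|---|---|---|---|
| Full verification (true) | 80% | 80% | 4.0 | 0.25 | 80% | 0.88 |
| 50% | 81–83% | 73–74% | 3.1 | 0.23–0.25 | 76–77% | 0.87 |
| 25% | 82–85% | 67–69% | 2.6–2.7 | 0.23–0.26 | 72–74% | 0.85–0.86 |
| 0% | 83–87% | 59–63% | 2.1–2.2 | 0.23–0.27 | 67–69% | 0.83–0.84 |

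At 25% challenged, one later PLR gives 81–83%/73–74% and seven give 83–86%/63–67%.

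**Which bias is larger.** At 25% challenged and k = 3, true 60%/60% becomes 66–70%/46–50%, so specificity loses more. True 65%/95% becomes 70–74%/90%, so sensitivity shifts by 5–9 points and specificity by about 5. A wider grid of 432 any-of-three scenarios used true Se 0.6–0.9, true Sp 0.7–0.9 and correlation 0.3–0.9. The direction held in all 432 and the specificity bias was larger in 413 (96%). In all 19 exceptions true sensitivity was at least 20 points below true specificity.

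**Second-device trigger.** If a second device's SVI and CI also trigger a challenge (assumed cross-device correlation 0.3–0.7), the pooled figures become about 81–83%/69–72% at 25% challenged and 81–84%/62–68% at none. The direction is the same and the size somewhat smaller.

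**First PLRs only.** Cancellation unrelated to the PLR result leaves 80%/80%. Suppose instead that 30% of the 25 PLR-negatives were cancelled (7.5 cases) and no positives. The complete pairs then give Se 20/23.5 = 85% and Sp 14/19 = 74%. Counting the cancelled cases as all responders gives Se 20/31 = 65%; counting them as all non-responders gives Sp 21.5/26.5 = 81%. The bounds are therefore 65–85% and 74–81%.

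**The case against.** The strongest reply is that the plan never says it will pool. The universal first challenge is an express safeguard, TRIAL # lets first PLRs be separated, and a blank challenge block shows that none was given. A reader might infer that the study is committed to a biased analysis, or that its data cannot support a sound one. The documents support neither. What stands against the reply is that neither the data sheet nor the statistical section states an analysis rule, while Objectives expects false negatives from the selected set. Figure 3, cited for the six-hourly PLRs, could not be seen; Statistical Analysis does not refer to it.

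A reader might also infer that specificity always suffers more than sensitivity. That is not established: the order can reverse when true sensitivity is well below specificity. Nor does a negative PLR necessarily look more reassuring. LR− has no consistent bias in the table, and NPV falls.

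The AUC shift is modest. By the Hanley–McNeil formula at AUC 0.88, the standard error from 25 responders and 25 non-responders is about 0.050. The total error of a pooled AUC (bias and sampling error, assumed design effect 1–2) is about 0.04–0.05 at 25% challenged and 0.056–0.064 at none. For AUC alone, restriction to first PLRs is therefore not clearly better. The stronger case for it is the operating point, mainly specificity in the 80%/80% setting.

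Finally, later verification depends largely on recorded SVI, CI and PP, so a corrected analysis of all assessments is defensible. It must assume that physicians' orders depend only on recorded data, and Risks and Benefits lists clinician gestalt among the grounds for a challenge.

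**Conclusion.** The concern holds conditionally. If all challenged assessments enter the ROC uncorrected, specificity is understated and sensitivity overstated relative to full verification of the same assessments. That direction follows from the challenge rule. The size does not, because it rests wholly on assumed accuracy, prevalence, correlations, number of later PLRs and frequency of physicians' orders. In the 80%/80% setting with three later PLRs and 0–25% of all-negatives challenged, specificity loses about 11–21 points, sensitivity gains about 2–7, and AUC falls by about 0.02–0.05. PPV does not move when responder prevalence is the same at first and later PLRs. A second-device trigger would shrink these shifts somewhat.

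This is more than missing detail: the two natural readings of the plan give different answers on its primary aim. The analysis set should be fixed before the data are analysed.

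**What to change.** In Statistical Analysis, state that:

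1. The primary ROC, sensitivity and specificity use each patient's first PLR and fluid-challenge pair, identified by TRIAL #.
2. Later PLRs are secondary and are used for PPV with patient-level clustering (for example GEE or a cluster bootstrap). Physician-ordered challenges after a negative PLR are reported separately as a selected sample. Any verification-corrected analysis of all assessments (for example Begg–Greenes or inverse-probability weighting) is a sensitivity analysis, with its assumption about what drives verification stated.
3. Cancelled first challenges are tabulated by PLR result, with bounds that count them first as all responders and then as all non-responders.

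The descriptions of the trigger in Objectives and in Study Methods and Procedures must be reconciled, so that the analysis knows which measurements led to a challenge. A data-sheet field for the reason for cancellation would help with item 3.

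**Cost.** Analysis wording and, if adopted, one data field; no fluid or treatment rule changes. There are two real downsides. The primary result describes the first assessment, not the whole ICU stay. It also rests on at most 50 pairs: the 95% half-width for an AUC of 0.80 is about 0.12 with 25 responders and 25 non-responders and about 0.14 with 17 and 33, and a sensitivity of 20/25 has a Wilson 95% interval of 61–91%.
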